4.2. Description and schedule of visits and procedures

Approximately 40 subjects with either OAG or OHT will be randomized, for a target of 36 completed subjects. Subjects will be randomized in a 1:1 ratio to receive 1 % Nyxol or placebo once daily for 14 days beginning at 8PM to 10PM on Day 1 and continuing through Day 14. Efficacy evaluations (IOP) will take place at the Baseline and the Treatment-study Visit days (Day 8 ± 1 Day and Day 15 ± 1 Day) at 8AM, 10AM, and 4PM. All IOP measurements have a window of ± 15 minutes with at least 2 hours between the 8AM and 10AM assessments. There will be Follow-up Visits on Day 16 at 8AM ± 15 minutes and by phone on Day 22 (7 days after the last Treatment-study Visit).

Study procedures are shown in detail in Table 1:

4.3. Measures taken to minimize/avoid bias

This is a double masked, placebo controlled study with 1:1 randomization.

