2. INTRODUCTION

2.1. *Investigational products*

The test product is Nyxol Eye Drops - 1% phentolamine mesylate ophthalmic solution (Nyxol), an alpha-1-adrenergic antagonist. Placebo control is Nyxol vehicle alone.

2.2. *Findings from nonclinical and clinical studies*

Detailed findings from nonclinical and clinical studies and potential risk are provided in the Investigators' Brochure (IB) (January 2019).

Single Dose Phase 2:

In NYX-SNV, treatment of 16 subjects with severe night vision disturbances with a single dose of 1% Nyxol resulted in [REDACTED]

Statistically significant improvements in several measurements of visual function as well as wavefront aberrometry were also reported. Modest, transient increases were seen in conjunctival and bulbar hyperemia.

Multiple Dose Phase 2:

In NYX-01a2, (Ocularis IND 70-499) 60 otherwise healthy subjects with reduced mesopic contrast sensitivity (CS), divided into three groups of twenty subjects each, received placebo, 0.5% or 1.0% Nyxol for 15 days, followed by an optional two week period where the subjects could use up to six doses of 1.0% Nyxol as needed.

IOP was measured 2 hours after the first dose on Day 1, and then again on Day 32 that was at least three days after the last dose. The mean absolute IOP and mean IOP changes post treatment on Day 1 were statistically significant between the treatment arms and the placebo arm.

[REDACTED]

More than 100 subjects have received active doses of Nyxol ranging from 0.2% to 1.0% in Phase 1 and Phase 2 clinical trials. There have been no serious adverse events. All treated subjects developed some degree of conjunctival hyperemia, an average of one point increase on a four point CCLRU scale (none, mild, moderate, severe). Most subjects went from mild to moderate. Three went from mild to severe. All redness resolved within 8 hours.

The anticipated benefits of the proposed study are reduction in IOP and improvement in the signs and symptoms of open angle glaucoma and ocular hypertension. The risks determined in previous ophthalmic studies are local hyperemia and conjunctival injection.

Systemic risks, principally tachycardia and hypotension, are known from parenteral administration of doses of 5 mg phentolamine mesylate (Regitine, Bedford, Ohio; see Regitine

Prescribing Information in IB) and local injectable administration of OraVerse (Novalar, San Diego, California; see OraVerse Prescribing Information in IB).

Design justification

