The two primary mechanisms to lower IOP include decreasing the amount of aqueous humor production in the eye and increasing the outflow of aqueous humor from the eye³. Phentolamine is a non-selective alpha-adrenergic antagonist acting on the adrenergic nervous system and inhibits contraction of the smooth muscle. For example, phentolamine mesylate inhibits contraction of the iris dilator muscle, resulting in a smaller pupil size.

Alpha-adrenergic antagonists, including phentolamine, have been previously shown to lower IOP via the aqueous humor production and uveoscleral pathway respectively. The major conventional outflow pathway though includes the trabecular meshwork (TM), a tissue with contractile properties and α -2-adrenergic receptors. It is well accepted that relaxing of the TM is the optimal IOP lowering solution. Thus, the non-selective α -antagonist Nyxol is likely to relax the TM and lower IOP via this major outflow pathway.

Treatment of glaucoma focuses on one of the major risk factors: intraocular pressure (IOP), the pressure of the aqueous humor in the anterior chamber of the eye. IOP is a balance between production (inflow) and outflow of aqueous humor into and out of the anterior chamber. Aqueous humor is produced by the ciliary body. Adrenergic agonists, such as epinephrine generally decrease production of aqueous humor³. Paradoxically, prazosin and phentolamine, both adrenergic antagonists, also decrease production of aqueous humor and lower IOP⁴.

The conventional outflow pathway for the aqueous humor includes - but is not limited to - the trabecular meshwork. The TM has smooth-muscle-like properties and is actively involved in aqueous humor dynamics through contractile mechanisms. Smooth-muscle-relaxing substances are known to increase outflow rates and reduce IOP without affecting the ciliary muscle, circumventing side effects such as accommodative changes or miosis⁵. Prazosin, an alpha-1-antagonist, has been shown to enhance uveoscleral outflow in rabbits⁶. Nyxol can potentially reduce IOP by increasing aqueous humor outflow via this pathway as well.

Previous clinical studies of Nyxol conducted in normal healthy subjects or subjects with severe night vision complaints have shown that single doses and treatments for up to 30 days have resulted in statistically significant reductions in IOP in normotensive subjects, with no significant local or systemic adverse effects².

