- Change and percent change from Baseline to Day 8, Day 15, and Day 16 in best corrected distance visual acuity (BCDVA) (ETDRS high contrast) (photopic and mesopic) at 8AM.

- Change and percent change from Baseline to Day 8, Day 15, and Day 16 in distance corrected near visual acuity (DCNVA) (ETDRS high contrast) (photopic and mesopic) at 8AM.
- Percentage of subjects achieving improvements from Baseline to Day 8, Day 15, and Day 16 in BCDVA and DCNVA (photopic and mesopic) of greater than or equal to 1 line, 2 lines and 3 lines.

All Secondary Endpoints related to IOP will be analyzed additionally in those subpopulations with Baseline IOP of $<25\text{mmHg}$ and $\geq 25\text{mmHg}$.

The lighting conditions will be kept the same from visit to visit. Every effort should be made to have the same clinician perform the IOP measurements at all timepoints and at all visits.

Safety:

The primary safety measures are objective biomicroscopic and ophthalmoscopic examination, subjective ocular tolerability, and adverse events (AEs). Other safety measures are systemic safety as measured by heart rate and blood pressure. Urine pregnancy tests for females of childbearing potential will be conducted.

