4.6. Randomization and procedure for breaking the code

A randomization code for allocating the study treatments will be prepared by a masked biostatistician not connected with the study.

At the initiation of study related procedures, every potential subject is assigned a **Screening number** in numerical order. Once a subject is qualified for the study (Qualification/Baseline Visit) the subject is assigned a **randomization number** in the order provided by the biostatistician.

The study medications will be masked to both Investigator and study subjects, as well as Ocuphire. Treatment assignments will be masked to the Investigator, Ocuphire, and the subjects. Only in case of medical emergency or occurrence of serious adverse events (SAE) will the randomization code be unmasked by the study pharmacist and made available to the Investigator, Ocuphire, and/or other personnel involved in the monitoring or conduct of this study.

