7. ASSESSMENT OF EFFICACY

7.1. Specification of the efficacy parameters

The primary efficacy endpoint is the change from Baseline to Day 15 in mean diurnal IOP. Mean diurnal IOP is the mean of the IOP measurements at all three timepoints (8AM, 10AM, 4PM).

IOP is measured with the Goldmann Applanation Tonometer, using a two-person method (one-person physically applies the tonometer, while another reads the result)¹¹.

The eye with the higher IOP at the Qualification Visit at 8AM is designated as the study eye. In the case where both eyes have the same IOP, the study eye will be the RIGHT eye. Baseline evaluations will occur before dosing on Day 1; Treatment-study evaluations will occur on Day 8 ± 1 Day and Day 15 ± 1 Day; follow-up evaluations will occur at 8AM on Day 16.

IOP measurements at the Baseline Visit and both Treatment-study Visits will be performed at 8AM, 10AM and 4PM. All IOP measurements have a window of ± 15 minutes with at least 2 hours between the 8AM and 10AM assessments. IOP will be measured twice in both eyes at each timepoint. The mean value at each timepoint for the study eye will be used in efficacy assessments. If the difference in the two IOP measurements is > 5mmHg, a third measurement will be obtained, and the three values averaged.

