7.2.4. Study Day 8 ± 1 Day

On Study Day 8, the subject should bring their used dropper bottles with any unused medications with them for purposes of drug accountability. At the end of the Study Day 8 Visit the study medication box will be re-dispensed with the unopened medication.

The subjects will be asked if they had any problems with their eyes from the last visit, and if there have been any changes in their medical condition, or concomitant medications since their last visit. ***Any changes in the condition of the subject are recorded as an adverse event.***

In addition, on Study Day 8:

- Review of concomitant medications at 8AM.
- IOP measurements will be done at 8AM, 10AM and 4PM. All IOP measurements have a window of ± 15 minutes with at least 2 hours between the 8AM and 10AM assessments. IOP will be measured twice in both eyes at each timepoint. The mean value at each timepoint for the study eye will be used in efficacy assessments. If the difference in the two IOP measurements is > 5 mmHg, a third measurement will be obtained, and the three values averaged.
- Pupil diameter, near and distance visual acuity, resting heart rate and blood pressure are measured at 8AM. Blood pressure, using the same arm, same cuff size appropriate for arm circumference throughout the study, and heart rate should be measured after at least 3 minutes rest in the sitting position. If HR or BP are outside the normal range (see Exclusion Criteria – Systemic #7 and #8), they may be repeated only once following at least a 5 minute rest period in the sitting position.
- Eye redness (conjunctival hyperemia) visually checked at each timepoint using [REDACTED] scale.
- Adverse Events will be reviewed at each timepoint.

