### **8.2. Protocol Deviations**

Major protocol deviations, as determined by a Sponsor blinded review of the data prior to database lock and unblinding of the study, may result in the removal of a subject's data from the PP Population. The Sponsor or designee will be responsible for producing the final deviation file; this file will include a description of the protocol deviation and clearly identify whether this violation warrants exclusion from the PP Population. This file will be finalized prior to database lock.

All protocol deviations will be presented in a by-subject data listing, with a flag to indicate if a deviation was considered major..

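### Pupil size can suggest the treatment arm, and no readable text keeps the person who reads the tonometer from the pupil, redness and adverse-event assessments

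*Protocol*

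**What the plan says.** Protocol 4.3, the section on measures against bias, is one sentence: "This is a double masked, placebo controlled study with 1:1 randomization". Protocol 4.6 adds that "Treatment assignments will be masked to the Investigator, Ocuphire, and the subjects". Both concern treatment codes and allocation. Neither deals with signs of treatment in the eye.

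Protocol 2.2 describes two such signs. On the pupil: "phentolamine mesylate inhibits contraction of the iris dilator muscle, resulting in a smaller pupil size". On redness in earlier trials: "All treated subjects developed some degree of conjunctival hyperemia, an average of one point increase". The same paragraph adds that all redness had gone within 8 hours.

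The primary endpoint is the change from Baseline to Day 15 in mean diurnal IOP (8AM, 10AM, 4PM) in the study eye. Protocol 7.1 specifies Goldmann applanation "using a two-person method (one-person physically applies the tonometer, while another reads the result". Protocol 4.1 asks for continuity: "Every effort should be made to have the same clinician perform the IOP measurements at all timepoints and at all visits".

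The other assessments fall in the same visits. For Day 8, Protocol 7.2.4 says "Pupil diameter, near and distance visual acuity, resting heart rate and blood pressure are measured at 8AM", and 7.2.5 schedules the same for Day 15, with pupil and acuity repeated at 4PM. Redness is graded and adverse events are reviewed at every IOP timepoint on both days.

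**The concern.** The placebo is vehicle alone, and no readable text says that it mimics the pupil effect. Someone who has just measured a clearly smaller pupil than at Baseline, or has heard a subject describe red eyes after each evening dose, has some information about the arm. If that person then reads the tonometer dial, a small tendency to read or round toward the expected result becomes possible.

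Such an error would favour Nyxol on the primary endpoint. Baseline is measured before any dose, so the cues exist only after treatment starts, and a shift at Day 15 passes in full into the change score. Randomization does not remove it, nor does ANCOVA on baseline IOP. It could not be corrected after the data are collected.

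**Working it through.** **1. The plan's own figure.** Protocol Section 1 gives 36 completers and about 10% drop-out: 36 / (1 − 0.10) = 40 randomized, as stated. The 36 itself cannot be reproduced, because the text giving its basis is redacted.

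**2. When each cue could be present.** Dosing is at 8PM to 10PM.
- From dose to the 8AM reading is 10 to 12 hours, or 9.75 hours at the edge of the ±15-minute window.
- Redness cleared within 8 hours in earlier trials, so on that figure it is gone at least 9.75 − 8 = 1.75 hours before the first reading of the day. What remains is redness that the subject reports.
- No readable text gives the size of the pupil effect 10 or more hours after dosing. The secondary endpoints count 8AM pupil reductions of at least 10% to 30% on Days 8, 15 and 16. The protocol is therefore looking for an effect at that hour, but this is not a forecast.

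**3. Who has the cues.**

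| Task | Timing | Who, in readable text |
|---|---|---|
| Apply tonometer | 8AM, 10AM, 4PM | One of two people |
| Read the dial | 8AM, 10AM, 4PM | The other of the two |
| Measure pupil | 8AM (also 4PM on Day 15) | Not assigned |
| Grade redness, review adverse events | 8AM, 10AM, 4PM | Not assigned |

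The visit lists put IOP ahead of pupil diameter but do not say that this is the required order within the 8AM session. In any order, the 8AM pupil result precedes the 10AM and 4PM readings, and the Day 8 result precedes every Day 15 reading.

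**4. What a reading shift would do.** Inputs from Protocol Section 1: 36 completers at 1:1, so 18 per arm; SD 3.0; two-sided t-test at 5%.
- SE of the difference = 3.0 × √(2/18) = 1.0 mmHg.
- df = 2 × 18 − 2 = 34; critical t = 2.032.
- With no true effect and an average between-arm shift b toward Nyxol, the rejection probability is P(|T| > 2.032), where T is noncentral t with df 34 and noncentrality b / 1.0.

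| Assumed shift b (mmHg) | Two-sided error | False result favouring Nyxol |
|---|---|---|
| 0 | 5.0% | 2.5% |
| 0.2 | 5.4% | 3.9% |
| 0.5 | 7.7% | 7.0% |
| 1.0 | 16.3% | 16.2% |

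By the same method, the difference detectable with 80% power is 2.88 mmHg. The three shifts are 0.2/2.88 = 7%, 0.5/2.88 = 17% and 1.0/2.88 = 35% of it.

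**5. Imperfect guessing.** If guesses about the arm are right with probability p, a shift d that would apply under perfect guessing becomes (2p − 1) × d. At an assumed p = 0.70 the factor is 0.40, so 0.5 becomes 0.2 mmHg (5.4%) and 1.0 becomes 0.4 mmHg (6.7%).

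**The case against.** The plan has more protection than Section 4.3 suggests. Codes are masked to investigator, sponsor and subjects, and one description of appearance covers both drug and vehicle. The person at the tonometer does not read the value. Repeat readings follow a fixed rule: two readings, a third only if they differ by more than 5 mmHg, and all three averaged. This stands, and it leaves little room within protocol for repeating and choosing a favourable value. It does not address how a reader who knows the pupil result reads or rounds the dial.

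Overlap of roles is also inferred. No passage says that the reader measures the pupil, and Table 1 and the IOP and pupil procedure cells, where a role split would most naturally appear, are redacted. This stands as a limit: if the split is stated there, a cross-reference in 4.3 closes the point.

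Three stronger readings are tempting, and the documents do not support them.
- *The pupil and redness reveal the arm.* The pupil effect at 8AM is not quantified, and the responder thresholds resemble those used for IOP, so they show interest and not an expected size. By the protocol's own figure, visible redness has gone before every reading.
- *The sponsor's deviation review is a second route to a biased primary result.* SAP 8.2 reads "Major protocol deviations, as determined by a Sponsor blinded review of the data prior to database lock", and no readable text limits what its reviewers see. But that review governs only the Per Protocol set, which SAP 7.1.2 makes confirmatory. The primary analysis uses the Full Analysis Set, defined by dose count and available IOP. Choosing an analysis set is also not observer bias.
- *A shift of 0.5 to 1.0 mmHg is likely.* It would have to be the average error across the three-timepoint mean, and it implies mostly correct guesses about the arm.

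**Conclusion.** The point holds as a gap in the readable plan, and not as evidence that the result will be biased. A pupil cue is plausible and is recorded at the visits that supply the primary endpoint. The endpoint is read by hand, with the same clinician wanted throughout. Nothing readable keeps the person who reads the dial from the pupil, redness or adverse-event information before that day's IOPs are recorded.

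The documents give no size for the bias. Across assumed shifts of 0.2 to 1.0 mmHg the two-sided error runs from 5.4% to 16.3%, and nearly all of the excess is at the 1.0 end. The figures rest on 18 per arm, SD 3.0, no true effect and a t-test. The planned ANCOVA would have a smaller SE to the extent that baseline IOP explains variance, and a given shift would then count for somewhat more. The change is worth making because it is cheap before the study starts and no analysis can replace it later.

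**What to change.** Add to Protocol 4.3 and 7.1:
- Of the two people already used for each IOP reading, the one who applies the tonometer, or other existing staff, measures the pupil, grades redness and takes the adverse-event history.
- The one who reads and records the dial does none of these and does not see those CRF pages until the day's IOPs are recorded. Since Day 8 pupil results would otherwise be known before Day 15, it is simplest to withhold the pages until the subject's last IOP is recorded.
- The 8AM IOP is taken before the pupil measurement.

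If the redacted procedure text already says this, a cross-reference from 4.3 is enough.

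The cost is a few lines of protocol text, a role line in the site instructions and a small scheduling constraint. No staff are added, and the sample size stays at 40 randomized for 36 completers. One weakness remains: the applier still sees the eye, so application technique is not shielded from the cues.

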4.4. Study medications

Nyxol (1%) is a sterile, non-preserved, isotonic, buffered aqueous solution containing phentolamine mesylate (1.0%), mannitol and sodium acetate. Placebo is Nyxol vehicle, consisting of non-preserved, isotonic, buffered aqueous solution containing mannitol and sodium acetate. The study medications may be adjusted with NaOH (USP) or HCl (USP) to pH 4.8. The product is packaged in a one ml LDPE dropper bottle containing 0.6 ml for single dose use.

4.4.1. Packaging and labeling

Nyxol (1%) and vehicle will be supplied as a clear, colorless to slightly brown, non-preserved aqueous solutions in one ml dropper bottles containing 0.6 ml. Each bottle will be labeled with investigational labels with the study number, subject initials and other relevant information, including a statement “Caution – New Drug – Limited by Federal (US) Law to Investigational Use”.

4.4.2. Storage of study medication

Prior to dispensing to the subject, all investigational material must be stored in a secure location with strictly limited access documented by signature of authorized persons who may dispense investigational materials. The products should be stored refrigerated (2°C to 8°C, 36°F to 46°F) until the day before use or until provided to the subject. Study medication must not be frozen and must be protected from light. The subject should be instructed that the product may be kept at room temperature once dispensed (up to 25°C, 77°F).

4.4.3. Study medication accountability

4.4.3.1. Receipt and disposition of study medication

The Investigator or designee (e.g., study coordinator or pharmacist) will maintain a full accountability record for the study medication and will be responsible for recording the receipt, dispensing, and return of all supplies of the study drug using the inventories supplied by the Sponsor. Each subject will receive sufficient study medication for the duration of the trial. A Study Medication Box will be dispensed at Baseline Visit (Day 1). As described in Section 7.2.3, the subject will empty any remaining contents from the unit-dose dropper bottle following each instillation and will return in baggies in the original boxes ALL opened bottles as well as any unopened study medication at Treatment-study Visits (Day 8 ± 1 Day and Day 15 ± 1 Day). At the Day 8 Visit, the box will be re-dispensed to the subject following study drug accountability and removal of opened study medication materials. Study medication accountability will again be conducted at the Day 15 Visit, but the box will not be re-dispensed. The Investigator or designee will account for all received and returned study medication. The monitor will review dispensing and study medication accountability records during site visits and at the completion of the study and note any discrepancies. All investigational study medication must be stored in a secure facility, with access limited to the Investigator and authorized staff.

4.4.3.2. Return of study medication

When the study is completed or is terminated by Ocuphire, all study material including used and unused study medication bottles will be returned to Ocuphire (or its designee) or destroyed under the direction of same. All study medication accounting procedures must be completed before the study is considered completed. A final study medication disposition will be completed by the study coordinator.

4.5. Expected duration of subject participation

The total length of subject participation is approximately 7-8 weeks with six clinic visits and one telephone call summarized below:

- Screening Visit (1 day).
- Washout Visit/period (as necessary) (4-5 weeks with safety check visit at 2 weeks).
- Qualification/Baseline Visit (1 day).
- Treatment-study Visit Day 8 (1 week).
- Treatment-study Visit Day 15 (1 week).
- Follow-up clinic Visit on Day 16 (1 day).
- Follow-up telephone call on Day 22 (1 week).

The execution of the entire study (first subject screen through last randomized subject completed) is expected to be approximately 6 months.

